The Emory University IRB, the OHRP, FDA, or other government regulatory authorities may perform clinical site monitoring. Clinical research sites monitoring may include the review of the individual participant records, including consent forms, CRFs, supporting data, laboratory specimen records, and medical records (physicians' progress notes, nurses' notes, individuals' hospital charts) to ensure protection of study participants, compliance with the protocol, and accuracy and completeness of records. The monitors may also inspect sites' regulatory files to ensure that regulatory requirements are being followed.

The investigators will make study documents (e.g., consent forms, CRFs) and pertinent hospital or clinic records readily available for inspection by the local IRB or the OHRP for confirmation of the study data.

ADVERSE EVENT MONITORING AND REPORTING

Adverse events (AEs) will be reported on an expedited basis at the standard level during the protocol-defined expedited adverse event (EAE) Reporting Period, which is the entire study

duration for an individual subject (from study enrollment until study completion or discontinuation of the subject from study participation for any reason).

AE Reporting

Any AE that is reported to either the investigators or their designated research associates by a study subject or by medical staff caring for the subject and which meets the criteria will be documented.

In addition, clinical investigators will monitor subjects for AEs during each study visit. Any AE will be reported to the Emory University IRB within 10 days of the event, and any serious adverse event (SAE) will be reported to the IRB within 24-48 hours of the event. The standard Emory IRB reporting guidelines for AE and SAE reporting, as documented at http://www.emory.edu/IRB/guidelines_adverse_event.php, will be followed.

A SAE is an adverse drug experience that results in any of the following outcomes:

1. Death.
2. Life-threatening situation - The subject was at risk of death at the time of the adverse event/experience. It does not refer to the hypothetical risk of death if the AE were more severe or were to progress.
3. Inpatient hospitalization or prolongation of existing hospitalization.

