4. Persistent or significant disability/incapacity - Any AE having an outcome that is associated with a substantial disruption of the ability to carry out normal life functions, including the ability to work. This is not intended to include transient interruption of daily activities.
5. Congenital anomaly/birth defects - Any structural abnormality in subject's offspring that occurs after intrauterine exposure to treatment.
6. Important medical events/experiences that may not result in death, be life-threatening, or require hospitalization may be considered a serious adverse event/experience when, based upon appropriate medical judgment, they may jeopardize the subject and may require medical or surgical intervention to prevent one of the outcomes listed above, i.e., death, a life-threatening adverse event/experience, inpatient hospitalization or prolongation of existing hospitalization, a persistent or significant disability/incapacity, or a congenital anomaly/birth defect. Examples of such medical events/experiences include allergic bronchospasm requiring intensive treatment in an emergency room or at home, blood dyscrasias or convulsions that do not result in inpatient hospitalization, or the development of drug dependency or drug abuse.
7. Spontaneous and elective abortions will be reported to the Emory IRB as serious adverse events.

8. Severity of AEs will be rated according to the following definitions:

Mild: The adverse event is transient and easily tolerated by the subject.

Moderate: The adverse event causes the subject discomfort and interrupts the subject's normal activities.

Severe: The adverse event causes considerable interference with the subject's normal activities and may be incapacitating or life-threatening.

The following definitions will be used to assess the relationship of the AE to study drugs or procedures:

Probably Related: An adverse event has a strong temporal relationship to study drug or recurs on re-challenge, and another etiology is unlikely or significantly less likely.

Possibly Related: An adverse event has a strong temporal relationship to the study drug, and an alternative etiology is equally or less likely compared to the potential relationship to study drug.

Probably Not Related: An adverse event has little or no temporal relationship to the study drug and/or a more likely alternative etiology exists.

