Not Related: An adverse event is due to an underlying or concurrent illness or effect of another drug and is not related to the study drug (e.g., has no temporal relationship to study drug or has much more likely alternative etiology).

If the adverse event is in, the investigator's opinion, possibly or probably related, or not related to study drug or procedures, then an alternate etiology will be provided by the investigator.

It should however be noted that a severe adverse event /experience is not necessarily serious, as the term severe is a measure of intensity while a serious adverse event (SAE) is determined based on the aforementioned regulatory criteria.

TITLE OF PROJECT: PrEP, LUBE, AND THE RECTAL MUCOSA IN MSM AT RISK OF HIV

Emory IRB00077593

PRINCIPAL INVESTIGATOR: [name], MPH

All AEs and laboratory abnormalities will be graded according to the Division of AIDS Table for Grading the Severity of Adult and Pediatric Adverse Events (DAIDS AE Grading Table), Version 1.0, December 2004, which can be found on the DAIDS RCC Web site: http://rcc.tech-res.com/tox_tables.htm. All AEs will be followed to satisfactory clinical resolution.

DATA SAFETY MONITORING

Summaries of adverse events (Grades 3 or 4), and targeted AEs across study groups as well as study conduct will be reviewed regularly (in real time and summarized quarterly) by study investigators. Any AE will be reported to the Emory University IRB within 10 days of the event, and any SAE will be reported to the IRB within 24-48 hours of the event. The standard Emory IRB reporting guidelines for AE and SAE reporting, as documented at http://www.emory.edu/IRB/guidelines_adverse_event.php, will be followed.

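### The relatedness categories and the SAE lead-in are worded for study drug only, so harm from the lubricant or the biopsies has no clear place in them

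*Protocol*

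**What the plan says.** Under Adverse Event Monitoring and Reporting, the protocol introduces its causality scale with a scope that includes procedures: "The following definitions will be used to assess the relationship of the AE to study drugs or procedures". Four categories follow:

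- Probably Related is defined by "An adverse event has a strong temporal relationship to study drug or recurs on re-challenge", with any other cause unlikely or clearly less likely.
- Possibly Related is defined by "An adverse event has a strong temporal relationship to the study drug, and an alternative etiology is equally or less likely".
- Probably Not Related is defined by "An adverse event has little or no temporal relationship to the study drug and/or a more likely alternative etiology exists".
- The lowest category, Not Related, is defined by "An adverse event is due to an underlying or concurrent illness or effect of another drug and is not related to the study drug".

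The sentence after the scale covers events judged possibly related, probably related or not related, again to drug or procedures, and ends "then an alternate etiology will be provided by the investigator". Seriousness is introduced by "A SAE is an adverse drug experience that results in any of the following outcomes".

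The section never mentions the lubricant. Elsewhere the protocol describes personal lubricants as devices (Risks of rectal lubricant application), gives one arm lubricant and nothing else (Visit 1), and uses the umbrella term study product for Truvada and lubricant together (Visit 3). All arms have rectal biopsies at visits 2 and 4, and product is first dispensed at visit 3.

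**The concern.** The scope sentence and the categories do not match. An assessor codes an event by matching it to a category, and no category can be met through timing to a biopsy or to the gel. The lubricant is worse placed than the biopsies: as a device it is neither a drug nor a procedure, so even the scope sentence does not reach it.

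Two things are at stake. The first is attribution: the protocol's risk text deals at length with tissue damage from lubricants and complications of biopsy, yet the scale cannot record either as a cause. The second is timing. Classification as an SAE decides whether an event is reported to the IRB within 24-48 hours or within 10 days, and the SAE lead-in is limited to drug experiences.

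**Working it through.** The plan gives no figure to reproduce, so the check is to apply the wording to the events the design can produce.

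**Relatedness, read literally**

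| Event | Timing to study drug | Other cause | Category met |
|---|---|---|---|
| Perforation after the visit 2 biopsy, any arm | None taken yet | Biopsy | Probably Not Related, on both limbs |
| Gel reaction, gel-only arm | None taken at all | Gel | Probably Not Related, on both limbs |
| Bleed after the visit 4 biopsy, a Truvada arm | Close | Biopsy, more likely | Probably Not Related, on the second limb |
| Reaction in the combined arm judged due to gel | Close | Gel, more likely | Probably Not Related, on the second limb |

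In the first two rows both related categories fail at once, because each asks for a strong temporal relationship to study drug (or, for the top category, recurrence on re-challenge). In the last two rows the timing test is met, but the true cause counts as the alternative etiology and takes the event out of the related categories. As a statement about Truvada that label may be correct. The fault is that there is nowhere to record that the event was related to the biopsy or the gel.

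Not Related does not fit these events, because it requires an underlying or concurrent illness or the effect of another drug.

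**How much of the design is exposed**

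Three arms at two biopsy visits make 3 × 2 = 6 combinations of arm and biopsy visit. No study drug has been taken in 3 of them (visit 2, every arm) plus 1 more (visit 4, gel-only arm), so 4 of 6. This counts exposures under a literal reading. It does not estimate how many events would be miscoded.

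**Seriousness**

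The lead-in restricts an SAE to a drug experience. The numbered criteria beneath it are outcomes, and the fourth (disability) and sixth (important medical events) are worded for adverse events generally. A hospitalisation for perforation after visit 2 matches the third criterion but not the lead-in. The text supports either classification, and the two carry different reporting clocks.

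**Whether by-arm summaries would compensate**

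For the gel, partly: the combined arm against the Truvada-only arm gives a contrast. For the biopsies, no: every arm has the same two procedures, so no arm serves as a biopsy-free comparator. Attribution of individual events therefore matters most for procedure harm. The SAP contains no safety analysis that would recover it.

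**Alternate etiology**

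The sentence asks for an alternate etiology for probably related events, where it makes little sense, and does not name probably not related events, where it is needed. For possibly related events the request is coherent, since that category is defined by weighing another cause.

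**The case against.** The strongest reply is that this is a drafting mismatch with little practical consequence. Procedures are expressly in scope, both in the scope sentence and in the sentence on alternate etiology, so a sensible investigator would read the categories accordingly. The SAE criteria are outcome-based, and the protocol later says that seriousness is determined by those criteria. Reporting of AEs and SAEs to the IRB carries no relatedness condition. The Medical Safety Monitor's report summarises AEs and SAEs by group and is not described as limited to related events. Participants are interviewed 24 to 48 hours after each biopsy about procedure-related problems.

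Most of that stands, and it rules out several stronger readings that a reader might infer:

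- That these events would be classed as Not Related. The illustration in that category, "is not related to the study drug (e.g., has no temporal relationship to study drug", invites this, but the definition also requires an illness or another drug.
- That they would be classed as not serious. The listed outcomes point the other way; only the lead-in creates doubt.
- That the Medical Safety Monitor's decision would be biased towards finding no related events. Nothing says that the report shows relatedness.
- That gel and biopsy are the main risks of the trial. The protocol does not rank risks, and it expects serious biopsy complications to be very rare.

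The reply does not remove the contradiction. Good sense can stretch the categories to procedures because the scope sentence invites it, but no wording in the section invites stretching them to the gel. Two assessors could code the same event differently and both be following the text.

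**Conclusion.** The concern holds as a definitional fault. The stated scope and the category wording disagree for biopsies, the lubricant is left out altogether, and the SAE lead-in is narrower than the criteria it introduces. Harm from the visit 2 biopsy, or from the gel in the gel-only arm, could be labelled Probably Not Related and could be put on the slower reporting clock.

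The size is limited to wrong or inconsistent labels and possible delay. The documents give no basis for an expected number of miscoded events. Nothing suggests that events would be hidden.

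Two assumptions matter. One is that assessors apply the category text literally, which is possible but not certain. The other is that the sentence sending any AE to the IRB governs, although the AE Reporting text also makes documentation of a reported AE depend on criteria that it does not specify. The CRF is not among the documents, so separate attribution may already be collected there.

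**What to change.** 1. In each of the four categories, replace study drug with study product (Truvada and/or lubricant) or study procedure, using the term already defined under Visit 3.
2. Define an SAE as any adverse event that results in one of the listed outcomes.
3. Record attribution to drug, lubricant and procedure separately for each event.
4. Correct the alternate-etiology sentence: require one for events judged probably not related or not related, ask that it be noted where one was weighed for a possibly related event, and drop the request for probably related events.

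The cost is wording in an amendment and one added CRF field. If events have already been coded, their attribution should be reviewed under the revised definitions before safety results are reported; that adds some investigator time but needs no new data collection from participants.

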TITLE OF PROJECT: PrEP, LUBE, AND THE RECTAL MUCOSA IN MSM AT RISK OF HIV

Emory IRB00077593

NCT02401230

PRINCIPAL INVESTIGATOR: [name], MPH

19Jan2018

STATISTICAL ANALYSIS PLAN

Drug and dNTP concentrations were normalized to fmol/million cells and fmol/mg rectal tissue in blood and tissue, respectively. Detectable drug and dNTP concentrations as well as immune cell proportions were compared between the Truvada, Rectal Gel Lubricant and Rectal Gel Lubricant + Truvada study arms using a Wilcoxon Rank Sum Test. Left censoring was observed for drug concentration measurements below the limit of detection.

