The efficacy reported in clinical studies of daily oral dosing of Truvada® or tenofovir to prevent HIV infection in MSM indicates the potential for PrEP to greatly reduce HIV infections within these high-risk populations. CDC recently released clinical practice guidelines recommending PrEP for MSM at risk of HIV infection.¹ However, the impact of rectal lubricant use on factors that could impact PrEP effectiveness in MSM is unclear. Recent studies suggest that lubricant application can increase epithelial damage and expression of inflammatory makers in human rectal tissue explants and epithelial cell cultures, and in macaque monkey rectal models without increasing their rates of HIV or SHIV infection, respectively.²⁻⁴ In contrast, consistent rectal lubricant use has been shown to increase acquisition of non-HIV STDs in a cohort of MSM in the USA.⁵ Additionally, studies from the TDF2 Study have suggested that ratios of intracellular tenofovir to natural substrate are reduced in the presence of immune cell activation. Together, these studies raise the concern that while MSM taking oral PrEP may be protected from HIV acquisition, regular use of rectal lubricants may abrogate the protection provided by PrEP due to increased epithelial damage, inflammation and immune activation.

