To address the impact of a popular, over the counter, gel lubricant use in the rectum in MSM on PrEP, investigators at Emory University will collaborate with [name] at the CDC to recruit and randomize 90 MSM into a three-arm study of PrEP and lubricants: (1) daily oral Truvada® for 7 days, (2) daily gel lubricant applied rectally for 7 days or (3) oral Truvada® plus rectal gel lubricant application daily for 7 days. At CDC, *ex vivo* laboratory assays will be used to evaluate the impact of rectal lubricant use on oral PrEP's effectiveness. Blood, rectal secretions and rectal biopsies obtained by rigid sigmoidoscopy (at approximately 8 -10 cm from the anal verge) will be collected from men in all three study arms at least 21 days prior to initiation of treatment and immediately following 7 days of consecutive use of assigned product. Specimens will be processed immediately for *ex vivo* laboratory assays at CDC. Blood plasma and PBMCs will be used to measure extracellular and intracellular drug concentrations as well as intracellular concentrations of the natural dNTP substrates to assess adherence to oral Truvada® and to compare changes in the ratio of drug to natural substrate in peripheral blood. Rectal secretions from all participants will be analyzed to measure changes in soluble immunological cytokines in the presence of gel lubricant usage that may indicate associated increases in inflammation. Rectal lymphocytes will be isolated from the rectal biopsies collected from each man and analyzed for concentrations of intracellular tenofovir and emtricitabine as well as natural substrates, dATP and dCTP, to evaluate the potential for gel lubricant to alter the ratio of antiretroviral drug to natural substrate in the rectal mucosa. Additionally, rectal lymphocytes from 10 participants in each arm will be characterized using multicolor flow cytometry to observe potential changes in the proportion and activation state of HIV target cells within the rectal mucosa. Rectal lymphocytes from the remaining 10 participants in each arm will be subjected to *in vitro* infection with HIV to test for changes in the susceptibility to virus infection in the presence of gel lubricant usage.

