These studies should provide important laboratory results to help inform policy and public health officials as to usage of hyperosmolar rectal lubricants in concert with oral PrEP. Pharmacological analyses will provide important data as to whether lubricant usage diminishes the ratio of drug to substrate in HIV target cells in the rectum that may reduce PrEP effectiveness. Immunological studies will help us understand whether lubricant usage

9/26/16

TITLE OF PROJECT: PrEP, LUBE, AND THE RECTAL MUCOSA IN MSM AT RISK OF HIV

Emory IRB00077593

PRINCIPAL INVESTIGATOR: [name], MPH

increases inflammation and the concentrations of HIV target cells in the rectum of men taking oral PrEP. The *ex vivo* virus infection assays described here will provide a surrogate measure of whether lubricant usage increases susceptibility to rectal infection with HIV for men taking oral PrEP. Together the combination of these studies should help determine if rectal lubricant usage may abrogate the potential anti-HIV benefits of oral PrEP.

Public Health Relevance: Information about the impact of rectal lubricant use in men who have sex with men will better inform policy makers and the public to make important choices regarding the safety of rectal lubricant usage in the presence of pre-exposure prophylaxis.

Goal: To determine if PrEP efficacy can be abrogated by use of rectal lubricants in MSM.

STUDY POPULATION

A total of 70 HIV-negative MSM aged 18-49 will be recruited from existing Emory University study databases of MSM who have agreed to future contact about research opportunities. We will also recruit men from print and on-line advertisements. Research recruiters at the Hope Clinic and the Rollins School of Public Health are experienced in recruiting this population for research studies, including those with rectal biopsies, and do not anticipate problems. [name] is currently conducting an Emory IRB approved study of the effects of unprotected anal intercourse on the rectal mucosa. This study involves recruiting a similar population to undergo repeated rectal biopsy procedures that are timed with sexual intercourse. We expect approximately 10-15% of men will not complete the study, therefore the sample size of 70 men will likely result in study completion for 60 men.

INCLUSION CRITERIA FOR MSM

- 1) HIV-negative man who reports receptive anal sex with another man in the last 6 months aged 18-49 years

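### Rectal drug and dNTP are reported only per mg of tissue, which does not by itself answer the protocol's question about drug relative to substrate inside rectal HIV target cells

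*SAP*

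**What the plan says.** The SAP is one paragraph. On units it says: "Drug and dNTP concentrations were normalized to fmol/million cells and fmol/mg rectal tissue in blood and tissue, respectively". On comparisons it says: "Detectable drug and dNTP concentrations as well as immune cell proportions were compared between" the three arms, "using a Wilcoxon Rank Sum Test". It lists no drug:dNTP ratio, no rectal per-cell value, no cell yield or count per mg, and no reason for using different units in the two compartments.

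The protocol's Project Description plans something different for the rectum: "Rectal lymphocytes will be isolated from the rectal biopsies collected from each man and analyzed for concentrations of intracellular tenofovir and emtricitabine", together with dATP and dCTP. It gives the purpose as "to evaluate the potential for gel lubricant to alter the ratio of antiretroviral drug to natural substrate in the rectal mucosa". The same section says that the pharmacological results will show "whether lubricant usage diminishes the ratio of drug to substrate in HIV target cells in the rectum". It also gives the rationale that "regular use of rectal lubricants may abrogate the protection provided by PrEP due to increased epithelial damage, inflammation and immune activation", and it makes a rise in rectal target cells one of the immunological questions.

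**The concern.** The core pharmacological contrast is Truvada against Truvada plus lubricant in the rectum. The protocol asks it at the level of the cell; the SAP answers it per unit of tissue weight. These agree only if the number of drug-bearing cells in a milligram is the same in both arms. The protocol gives its own reasons to doubt that, because the lubricant under test is suspected of drawing in target cells and damaging epithelium.

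If cells per mg do differ, the per-mg test mixes two mechanisms that the Lay Summary sets out separately: more target cells, and less drug. An influx could mask a real fall in drug per cell, and a loss of cells could look like a fall in drug that did not occur. Testing dNTP per mg separately carries the same problem, since more cells per mg would look like more competing substrate. The protocol intends the results to inform policy on lubricant use with PrEP, so the label on the rectal result matters.

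**Working it through.** The plan gives no power, effect size, SD, alpha or cellularity figure for this comparison, so there is no stated result to reproduce on the point itself. The only planning figure used below is the number of completers. Study Population gives 70 recruited, 10–15% dropout and about 60 completers: 70 × 0.85 = 59.5 and 70 × 0.90 = 63, so it reproduces, and 60/3 = 20 per arm with equal arms. (The Design paragraph says 90 men; the difference needs reconciling but does not affect this point.)

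**1. Identity.** Drug per mg ≈ (drug per cell) × (drug-bearing cells per mg).

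**2. Break-even.** If cells per mg rise by a fraction d, the per-mg value is unchanged when drug per cell falls by 1 − 1/(1+d). The values of d are assumed.

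| Rise in cells per mg | Per-cell fall concealed |
|---|---|
| 25% | 1 − 1/1.25 = 20% |
| 50% | 1 − 1/1.50 = 33% |
| 100% | 1 − 1/2.00 = 50% |

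**3. The matrix matters.** The SAP does not say what was assayed.
- If isolated lymphocytes were assayed and the result divided by biopsy weight, the second factor is lymphocyte yield per mg, and the table applies to that yield directly.
- If whole tissue was assayed, target cells are only part of it. Suppose they are a share s of drug-bearing cells, with equal drug in every cell. Doubling them then raises total cells per mg by s. For s = 10% the concealed fall is 1 − 1/1.10 = 9%; for s = 20% it is 1 − 1/1.20 = 17%.

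**4. Effect on the planned test (illustration).** Assumptions: rank sum test, two-sided 0.05, 20 per arm, log-normal data with log-scale SD 0.7 (range 0.4 to 1.0), the same spread on either scale, all values detectable, 4,000 simulated trials.

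| Truth with lubricant | Per-mg test finds a loss | Per-cell test finds a loss |
|---|---|---|
| Drug per cell halved, cells/mg × 2 | about 3% (chance level) | 85% (about 100% to 54%) |
| Drug per cell halved, cells/mg × 1.5 | 22% (58% to 13%) | 85% |
| Drug per cell unchanged, cells/mg × 0.7 | 33% (76% to 20%) | about 2.5% (chance level) |

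No cell-counting error was added, so the per-cell column is optimistic.

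**5. The drug:dNTP ratio.** If both analytes come from the same sample, (drug per mg)/(dNTP per mg) = drug/dNTP, so weight and total cell number cancel. Cell mix does not. In a two-compartment mix (lymphocytes and other cells), with the ratio in other cells set at 0.33 to 3 times that in lymphocytes:
- doubling the lymphocyte share (10% to 20%, or 20% to 40%) with no loss in any cell type moves the tissue ratio to between × 0.78 and × 1.29;
- with a fixed 10% lymphocyte share, a 50% loss in lymphocytes appears as only × 0.75 to × 0.98.

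The ratio therefore removes one source of bias but does not turn a tissue result into a target-cell result.

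**The case against.** The strongest reply has five parts.

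- **The main rectal aim is a ratio, and total cellularity cancels in a ratio.** This is correct, and it means that the protocol's question should not be read as intracellular concentration alone. It does not protect the SAP as written, because the SAP lists drug and dNTP concentrations and no ratio.
- **Tissue drug level is also a stated aim.** The Design paragraph asks about drug concentrations, and the Lay Summary speaks of rectal tissues with lower drug levels. This stands: fmol/mg is a legitimate result for that aim and should be kept. It does not support the separate conclusion about HIV target cells.
- **Whole-tissue assay is inferred.** This also stands. A reader might take the unit as proof that whole-tissue homogenate was measured; the SAP does not say so. Under either reading the per-mg value depends on cells or yield per mg.
- **The assumed cellularity changes are not in the documents.** This stands. The protocol hypothesises more target cells, described in places as a proportion, not a given change in all drug-bearing cells per mg. Tissue swelling, which a reader might add as a route to a false drug loss, appears in neither document.
- **The per-cell value is not neutral either.** This stands. The composition and activation of the isolate may also respond to lubricant.

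The immune cell proportions do not fill the gap. A proportion is not a count per mg, and the protocol plans flow cytometry in only 10 participants per arm.

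**Conclusion.** The point holds as an unexplained departure of the SAP from the protocol's rectal measurement. As written, the analysis gives rectal tissue content and does not by itself support a conclusion about drug relative to substrate in HIV target cells.

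The size and direction of any bias cannot be determined from the documents. The 20% to 50% concealed falls and the simulated error rates rest on assumed cellularity changes, spread and alpha, and show only what is possible. A reader might infer that the per-mg comparison is biased or invalid, or that lubricant is known to alter cells per mg. The documents support neither: they make such a change plausible through the protocol's own hypotheses and report none. The mismatch of units is certain; the mechanism and its importance are moderately supported at most.

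**What to change.** 1. State which rectal matrix was assayed: isolated lymphocytes or whole tissue.
2. Where a cell count was recorded with the drug sample, report drug and dNTP per million isolated rectal cells alongside fmol/mg, and show cells per mg by arm.
3. Add the within-sample drug:dNTP ratio, which the Project Description names as the purpose of the measurement, to the comparison of Truvada with Truvada plus lubricant.
4. If no cell counts exist, describe the result as rectal tissue content, note the departure from the protocol, and drop the claim about HIV target cells.

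No new study procedure is needed. The ratio requires only that both analytes were measured in the same sample. The per-cell step may not be available: neither document mentions rectal cell counts or yields, and the SAP, dated 19 January 2018, describes the analysis in the past tense, so counts may not be recoverable and step 4 may be the only option. Per-cell values also add counting error, and low-yield isolates may be missing. Both the per-cell value and a tissue-level ratio still depend on the cell mix, which lubricant may alter, so the report should say so.
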